In a pilot study investigating pairing locomotor training with transcranial direct current stimulation in patients with chronic stroke²³, our research collaborator at the University of Kentucky, [name], conducted a double-blind, randomized trial of active and sham tDCS (20 min at 2mA anodal stimulation over motor cortex) delivered just prior to locomotor training using a robotic gait orthosis treadmill. Eight participants (4 men, mean age=67.8; range=44-80) with chronic left hemisphere stroke (mean years post-stroke=4; range=1.1-11.6) were tested. Performance on a 10-meter walk test was the primary outcome measure, and assessments of functional ambulation category (FAC), timed up and go, balance, and the 16 item Stroke Impact Scale (SIS 16) were secondary measures. Improvement on the 10-meter walk test and the SIS 16 following active tDCS are shown in the figure - right. Active tDCS lead to greater improvement than sham tDCS on the FAC ($p=0.028$) and similar trends were evident for the SIS 16 ($p=0.062$) and the timed up and go test ($p=0.066$). This study shows that active tDCS augments gait training and function. The data were also used for power calculations.

Hypothesis and Specific Aims

Hypothesis: Increasing cortical excitability with active anodal tDCS prior to gait training will augment recover from a stroke.

Specific Aims:

1. Determine if active tDCS augments gait. Gait speed is a primary outcome measure. Spatiotemporal and kinematic gait assessment are secondary measures of gait. Over ground laboratory assessments of gait will measure 1) gait velocity and spatiotemporal gait measures using the GAITRite electronic walkway 2) ankle, knee, and hip angles using the SIMI motion analysis system. Changes in gait parameters will be expressed as difference scores from baseline. Difference scores will be compared between the active and sham groups to determine if tDCS augments gait parameters.

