2. Determine if active tDCS augments cortical excitability after gait training. Cortical excitability will be defined by a cortical recruitment curve, a primary outcome measure, derived from plots of motor evoked potentials (MEPs) recorded from the ipsilesional TA muscle. MEPs are elicited by single pulse transcranial magnetic stimulation (TMS) delivered at increasing intensity over motor cortex. Changes in the slope of the recruitment curve signal change in cortical excitability. Difference scores from baseline will be compared between active and sham groups to determine if tDCS augments cortical excitability after FESAGT. A repeat fMRI will be performed to assess change in cortical excitability after gait training.
3. Determine if active tDCS augments physical function and social wellbeing. The Stroke Impact Scale-16 (SIS-16), a primary outcome measure, will be used to assess ADL/IADL, mobility, and social and occupational engagement at baseline and post treatment assessments. Difference scores from baseline will be compared between active and sham groups to determine if tDCS augments physical function and social well-being.

Exploratory Aim

Identify patient characteristics that predict response to treatment. Patients will be classified empirically based on their response to treatments. Regression analyses will examine whether and how initial impairment, functional level, and cortical excitability predict a treatment response.

Study Interventions

tDCS and gait training will be conducted at UCA three times a week for 4 consecutive weeks

Version 10 Revised 11/21/2014

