Prior to the MRI scan, subjects may have a training session in the MRI simulator to help habituate and train them to the MRI environment. Per the MRI Policies and Procedures, the decision of who will be acclimated in the MRI Simulator will be made by the Research Coordinators and PI on a case-by-case basis. The PI for the study will have final say in this decision. Before the MRI scan, participants will be given an explanation of the study's procedures and screened with the MRI Safety Form for metal objects and claustrophobia. Participants will also be screened with the SAFESCAN® ferromagnetic detector according to MRI Policy and Procedures. The participant will then lie supine in the scanner. Participants will wear noise-cancelling headphones for communication and view visual stimuli through a mirror attached to the imaging head coil. Participants will undergo an anatomic scan to facilitate alignment of electrodes. Participants will also have a resting state scan in which they will be told to simply let their mind wander while they lay still in the scanner. Participants will also complete a scan measuring TA contraction. Subjects will be asked to contract the TA muscle in their right and left legs periodically depending on stimuli presented to them. Participants will have an identical repeat fMRI scan after completing the gait training protocol. Total scan time will be approximately 20-30 minutes per scan.

Randomization Procedures

After consenting, screening, and obtaining an MRI, participants will be block

Version 10 Revised 11/21/2014

randomized into groups (20 minute tDCS group + gait training or sham tDCS + gait training).

Baseline Procedures

The TMS motor threshold (MT) will be established²⁷ and the best location for eliciting MEPs from the contralesional TA muscle will be tracked on the subject's CT or MRI scan, or on a template MRI scan if clinical studies are not available, using Brainsight. Gait assessment (details provided in **Outcome Measures**) and the Stroke Impact Scale-16 will be performed for all participants at UCA. Motor evoked potentials and Recruitment curves (developed by the TMS procedure) will be performed at UAMS.

Intervention Procedures (Study Weeks 1 through 4)

Study interventions will be conducted 3 times a week for 4 continuous weeks. tDCS, and gait training will be performed at Movement Analysis Laboratory, Department of Physical Therapy, UCA as described above (**Study Interventions**).

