Post-Intervention Procedures (Study Weeks 5(± 5 days) and 8 (± 10 days) :

During Study Weeks 1-5, and 8 Gait assessment (details provided in **Outcome Measures**) and the Stroke impact Scale 16 will be performed at UCA. During Study Weeks 5 and 8 TMS will be performed at UAMS and participants will complete a repeat fMRI scan. Details of TMS procedure used to establish recruitment curves are located in the Outcome Measures.

Reduction of Study Bias:

[name] will supervise delivery of interventions, and so, he will not be blinded to tDCS condition; however, Drs. [name] and [name] who collect and analyze data will be blinded to condition.

Study Locations:

tDCS, gait training, SIS-16, and the assessments of gait will take place in the Motion Analysis Laboratory at UCA; motor evoked potentials and recruitment curves developed from TMS are measured in the TMS and Human Electrophysiology core facilities at UAMS. Subject burden is reduced by requiring only four trips to UAMS over two - three months. (Subjects are informed that scheduling conflicts could result in an extra visit.) UAMS will be the IRB of record and Sponsor of the IDE.

Study Schedule

	Screening	Baseline	Study Weeks 1 -4 ^b	Study Week 5	Study Week 8
Consent	X				
Screening	X				
NIH Stroke Scale	X				
Modified Rankin Scale	X				
TASS	X				
Medical Record Review	X				
MRI	X			X	
Pregnancy Assessment	X				
Randomization	X				
Assessments					
Gait assessments		X	X	X	X
RC & SIS		X		X	X
Interventions					
tDCS			X		
Sham tDCS			X		
Gait training			X		

Definitions: TASS= Transcranial Magnetic Stimulation Adult Safety Screen, MRI=magnetic resonance imaging, RC & SIS-16=recruitment curve established using transcranial magnetic stimulation (TMS) and Stroke Impact Scale . ^bThree times a week for four weeks participants will receive active or sham tDCS and gait training interventions at UCA for a total of 12 treatment periods.

Study Population

Up to 100 stroke patients will be enrolled to obtain 88 who meet entry criteria and complete study procedures (i.e., 44 participants in each of the active or sham tDCS groups). Attrition, estimated at about 15%, will be handled by replacement.

Participants will be ≥21 years old to better represent the general stroke population. All participants will complete the NIH Stroke Scale, have evidence of gait impairment, and will be able to fully and safely participate in treatment.

Inclusion Criteria

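### Randomisation is placed at screening, before the baseline measures that every primary difference score needs, so anyone lost between allocation and baseline is an avoidable post-randomisation exclusion

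*Combined protocol and SAP*

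**What the plan says.** **Order of events.** Randomization Procedures states: "After consenting, screening, and obtaining an MRI, participants will be block" randomised into the active or sham group. No baseline assessment is listed as a precondition. The section that follows, Baseline Procedures, covers motor threshold, gait, SIS-16 and recruitment curves. In the Study Schedule the row "Randomization X" has its single mark in the Screening column. Gait, and recruitment curve with SIS, are first marked in the next column, Baseline.

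**Where baseline is done.** Gait assessment "and the Stroke Impact Scale-16 will be performed for all participants at UCA", and "Motor evoked potentials and Recruitment curves (developed by the TMS procedure) will be performed at UAMS". Completing baseline therefore means attending both sites.

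**Use of baseline.** Specific Aims names three primary outcomes. For Aim 1, "Gait speed is a primary outcome measure". For Aim 2, "Cortical excitability will be defined by a cortical recruitment curve, a primary outcome measure". Aim 3 gives SIS-16 the same status. Data Analysis calculates a difference from baseline for every outcome.

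**Losses.** Study Population plans up to 100 enrolled to reach 88 who meet entry criteria and finish, 44 per arm. It adds: "Attrition, estimated at about 15%, will be handled by replacement".

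**Blinding.** Reduction of Study Bias says that the intervention supervisor "will supervise delivery of interventions, and so, he will not be blinded to tDCS condition". The same sentence goes on to say that those who collect and analyse the data are blinded.

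**The concern.** A randomised comparison is protected when everything measured before treatment is fixed before allocation. Here half of each primary outcome is collected after allocation, which opens two routes to trouble.

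1. **Missing baseline.** Someone randomised who never completes baseline has no difference score on the affected outcomes. The plan defines no intention-to-treat set and no rule for this case. If the person has left the study, the attrition rule replaces them. They then disappear from the comparison after allocation, and blinding the assessors does not prevent it.
2. **Influenced baseline.** If allocation becomes known before baseline, expectation or encouragement could shift the baseline value, and a difference score carries that shift in full. This is a possibility only, and the smaller of the two.

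**Working it through.** The point concerns sequence, and the plan states no figure to reproduce. The check compares the sections and then bounds what can be bounded.

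**Step 1: is the order consistent?** The Randomization Procedures text and the Study Schedule agree, and no other section places randomisation after baseline. This is the plan as written, not a slip in one place.

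**Step 2: does every primary outcome depend on it?** Gait speed, recruitment curve and SIS-16 are all listed under Baseline Procedures, all marked first under Baseline, and all analysed as differences from baseline. The first MRI does precede randomisation, but it is not a primary outcome.

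**Step 3: could baseline be incomplete?** The protocol itself gives reasons why it might be, though no rates:
- Baseline is split between two sites.
- The preliminary work reports that the first recruitment-curve technique worked in one of three stroke participants. The curve has since moved to the intact hemisphere, so this shows a hazard and not an expected rate.
- The Risks section ends TMS testing for a subject who shows signs of possible seizure or syncope.

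**Step 4: how many could be lost before baseline?** Let s be those who fail screening before randomisation, b those lost between randomisation and baseline, and a those lost after baseline. If 88 complete out of at most 100 enrolled:

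s + b + a ≤ 100 − 88 = 12, so 0 ≤ b ≤ 12.

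The upper end needs s = a = 0. The lower end holds whenever all losses are screen failures or come after baseline. Nothing in the documents narrows the range. The 15% attrition figure does not help: 0.15 × 100 = 15 losses would leave 85, short of 88.

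**Step 5: what would an allocation-related baseline shift do?** If baseline differs between arms (active minus sham) by δ because of allocation, and follow-up values are unaffected, the difference-score contrast equals the true effect minus δ. The whole shift passes through.

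A what-if calculation uses 44 per arm, the plan's r = 0.60, one follow-up and a two-sided 5% test:
- SE in baseline SD units = √(2 × (1 − 0.60)) × √(2/44) = 0.894 × 0.213 = 0.191.
- Type I error = Φ(δ/SE − 1.96) + Φ(−δ/SE − 1.96).

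| Assumed shift δ (SD) | δ/SE | Type I error |
|---|---|---|
| 0.05 | 0.26 | 0.058 |
| 0.10 | 0.52 | 0.082 |
| 0.20 | 1.05 | 0.182 |

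These shifts are assumptions. The documents suggest no shift of any size, so the table shows sensitivity and is not evidence of bias.

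**The case against.** The strongest reply is that little harm follows from the order, and much of that reply stands.

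- **Blinding.** Those who collect and analyse data are stated to be blinded. At baseline no participant has had an assigned active or sham session, and the background section says sham can be given without detection. This substantially reduces the influence route. It does not close it: allocation concealment is not described and participant blinding is not stated (consent pages are not available for this review).
- **The unblinded supervisor.** A reader might infer that he affects the baseline values, because gait and SIS-16 are measured at the site where he works. The documents do not support that. His unblinding is tied to delivering the interventions, which start in Study Week 1. No section has him taking baseline measures, and names are removed, so his role cannot be checked. The recruitment curve is measured at the other site.
- **The measures differ in exposure.** Gait speed comes from an electronic walkway over five self-paced walks, which limits assessor influence. SIS-16 is completed by the study team and is the most exposed.
- **Losses need not differ by arm.** A reader might infer that losses before baseline bias the comparison. With blinding intact and no assigned treatment given, nothing in the documents shows that they would depend on arm. Their certain effect is that randomised people leave the comparison.
- **Replacement is the wider problem.** This is true. Replacing dropouts without an intention-to-treat set affects losses at any time, and changing the order deals only with those before baseline.

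What the reply does not answer is why allocation should come before baseline at all. Nothing before Week 1 needs it. The baseline test of the response to anodal tDCS, described with the preliminary work, is not presented as arm-specific.

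**Conclusion.** The concern holds as a point of sequence. Both the text and the schedule randomise before the baseline measures on which all three primary difference scores depend. Anyone lost in between is randomised, cannot be analysed as planned, and is replaced. This is certain from the documents.

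Its size is not known. The number lost between allocation and baseline lies between 0 and 12, assuming that the enrolment ceiling of 100 and the 88 completers both hold. A reader might apply 15% to 100 and count 15 losses, about 5 of them before baseline if a third fell there. The documents do not support either number: 15 exceeds the 12 that the enrolment plan allows, some non-completers may fail screening before randomisation, and no timing of attrition is given.

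Influence of allocation on baseline remains a lesser possibility, mainly for SIS-16. It rests on what the plan leaves unstated about concealment and participant blinding, not on any sign that it would occur. The change is worth making because it costs almost nothing, not because bias has been shown.

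**What to change.** Reword the Randomization Procedures sentence along these lines: *Participants will be block randomized only once consent, screening, the MRI and all baseline gait, SIS-16 and TMS assessments have been completed.* In the Study Schedule, move the Randomization mark from Screening to a point after Baseline and before Study Week 1.

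The cost is one sentence and one table mark. No visits are added, since allocation is first needed at the first treatment session. Because baseline is split between two sites, someone must confirm that both parts are complete before the allocation is released.

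If the present order has to stay, the plan should at least state how allocation is concealed, who is blinded at baseline, and how a participant randomised without a baseline is analysed.

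Replacement of participants lost after baseline is a separate issue that this change leaves untouched.

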Study: We will block randomize 88 chronic stroke patients to two treatment arms. Persons will be block randomized into anodal and sham tDCS conditions. Persons in the anodal tDCS condition will receive 20 minutes of stimulation and persons in the sham condition will receive 20 minutes of sham stimulation. All patients will receive gait training using a body weight supporting treadmill. In over ground assessments at baseline, weekly during gait training sessions, and one week, and one month post treatment, we will measure 1) gait velocity and spatiotemporal gait parameters using the GAITRite electronic walkway and 2) ankle, knee, and hip angles using motion analysis to gauge changes in the gait pattern. Cortical excitability will be measured at baseline, one week, and one month post treatment using transcranial magnetic stimulation (TMS). Functional MRI will be measured at baseline and after treatment between weeks 5-8. Additionally, we will measure change in physical function and social well-being using the Stroke Impact Scale and we will define patient characteristics that are associated with response to treatment.

Significance: If successful, this study will augment gait recovery and potentially increase the number of patients who benefit from gait training. Our methodological innovations will have application to a wide variety of neurological conditions.

Background and Rationale

Stroke is the leading cause of disability in the United States affecting 13 million people¹,². Up to two thirds of stroke survivors have significant limitations impairing their ability to walk³ including slow gait speed⁴ and changes in the quality of the gait pattern⁵. Additionally, individuals with a stroke and limited mobility are at high risk for subsequent complications including falls⁶, fractures⁷, and a further decline in mobility⁸. In contrast, recovering the ability to walk greatly improves quality of life and can return individuals to a previous level of productivity⁹⁻¹². Our proposal aims to use tDCS to

[figure not shown]
Version 10 Revised 11/21/2014

“jump start” the beneficial effect of gait training. This proposal is responsive to research priorities of the NINDS.

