Study Aim 2: Recruitment curves. A Magstim 200 super rapid2 stimulator with a 110 mm double cone coil will deliver stimulation. First, the TMS motor threshold (MT) will be established²⁷ and the best location for eliciting MEPs from the contralesional and ipsilesional TA muscle will be tracked on the subject's MRI scan in Brainsight. EMG will be recorded from the TA muscles of both limbs. The MT will be determined by placing the TMS coil over the cortical motor area and delivering single pulses of increasing intensity until the optimal area of stimulation is found. Threshold will be defined as the percentage of the maximum stimulator output necessary to elicit a motor evoked potential (MEP) of 50 μ volts recorded from the tibialis anterior muscle of the contralateral leg in 3 of 6 stimulus trials. Motor thresholds for both the lesioned and non-lesioned brain hemispheres will be recorded.

Second, recruitment curves will be obtained as follows: 1) delivering ten, single TMS pulses beginning at 70% of MT, 2) increasing TMS intensity by 10% and repeating the process up to 160% of the MT or until a plateau in the recruitment curve is reached, 3) offline data processing will be performed with the Matlab curve fitting toolbox and 4) the

threshold, slope, and MEPmax, and the goodness of fit (R^2) will be calculated. A change in the slope of the recruitment curve will indicate change in cortical excitability.

Study Aim 3: Functional and social assessments. The Stroke Impact Scale-16 (SIS-16, completed by study team) is a standardized instrument³⁶⁻³⁸ that assesses 3 functional domains in stroke patients including ADL / IADL, mobility, and social and occupational engagement.

Compensation

Participants will be remunerated \$200 for completing the entire study protocol. They will be remunerated \$75 dollars for partial completion.

Risks

A potential risk for study participation is the potential loss of confidentiality. Measures to protect the confidentiality of study participants will be implemented as described in the Data Handling and Recordkeeping section below.

Device Risks:

Potential risks associated with tDCS include the following:

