2. All subjects will wear ear plugs during testing sessions. TMS will be stopped if an ear plug falls out during a session.
3. A study physician trained in rescue procedures, will be on call when a subject is receiving single pulse TMS in this study. The study physician will be called by study personnel in the event of muscle contractions persisting after TMS (possible seizure) or complaints of dizziness, nausea, shortness or loss of breath, or loss of consciousness (possible syncope). Study personnel will note body parts that might be affected (e.g., the left arm or leg after right hemisphere stimulation) and/or other symptoms that might occur and report them to the

Version 10 Revised 11/21/2014

study physician. [Should these be observed, the session will be terminated, and the subject will not be tested again].

4. If a subject were to have a seizure or syncopal episode during or immediately following TMS, the following precautions will be performed by study personnel:
 - a. The stimulator will be stopped and the coil will be removed from the subject's head.
 - b. The subject will be supported to physically guard against injury.
 - c. The subject will be placed on his/her side on a flat surface away from sharp edges.
 - d. The study physician will be called.
 - e. Emergency services will be called by study personnel to transport the subject to the emergency room if so directed by the study physician.
 - f. Emergency services will be called if the study physician cannot be reached.
 - g. Either the study physician or the PI or subinvestigators will accompany the subject to the ER and explain the recommended post-event assessment which is as follows:

It is recommended that after the seizure is over, the subject will be examined thoroughly for injuries and a complete neurological exam will be completed. Routine studies, including calcium, magnesium, and prolactin, will be completed and urine will be sent for a drug screen. An MRI scan of the head will be performed to rule out underlying epileptogenic pathology. An EEG will be performed with hyperventilation and anterior temporal leads. The subject will be advised that following a seizure provoked by TMS, the likelihood of further spontaneous seizures is not significantly increased unless other pathology is discovered. The subject will be scheduled for a neurology consultation. The subject will not be allowed to drive himself/herself home. Transportation would be arranged for the subject.

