- Necessitates medical or surgical intervention to preclude a permanent disability or incapacity
- Results in a congenital anomaly or birth defect

Non-serious adverse events are all events that do not meet the criteria for a “serious” adverse event.

Severity:

Each adverse event will be assessed for its severity, or the intensity of an event experienced by the subject, using the following.

- Mild: Discomfort noticed, but no disruption to daily activity.
- Moderate: Discomfort sufficient to reduce or affect normal daily activity.
- Severe: Inability to work or perform normal daily activity.

Anticipated Adverse Events and Pre-existing conditions:

Pre-existing conditions will not be reported as an adverse event unless there has been a substantial increase in the severity or frequency of the problem which has not been attributed to natural history.

Data Handling and Recordkeeping

Each subject's name, birth date, address and phone number will be obtained for purposes of follow-up. We will ask for each subject's drug use history, medical history, and current drug use. Experimental data and questionnaire data will be collected. This information will be coded into the Microsoft Excel. Each subject's personal information will be de-identified in the database by using codes comprising the subject number and date and time the subject was tested. The PIs and study personnel at UAMS and UCA will have access to subject identities in order to arrange follow-up and to call them as part of the research project, such as follow-up contact. If subjects prefer e-mail correspondence research personnel will send e-mails for scheduling, follow-up, and research-related communication.

Data Analysis

Aims 1-3. Difference scores from baseline will be calculated for each outcome measure. A mixed model ANOVA with group (active tDCS groups versus sham tDCS) as the between subjects factor and time of assessment (pre, weeks 1-4, & one week and one month post) as the within subjects factor will be used to test all aims. A significant group effect, with active tDCS > sham tDCS, for any of the outcome measures would indicate that anodal tDCS augments gait training. A significant main effect of time would be evaluated using planned contrasts where we expect post treatment assessments to be improved relative to baseline. Interim analyses will be completed at critical stages during the protocol.

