Power analysis: We aim to determine whether tDCS can augment the beneficial effect of gait training. Our preliminary study using tDCS to improve gait velocity and the SIS16 score yielded very large effect sizes for walking speed (2.95) and the SIS16 (1.32). In real terms, patients who received active tDCS reduced their time to walk 10 meters by about one minute (this could shave 5 minutes off a task, like getting mail, so it is functionally significant); whereas those who received sham reduced their time by only 10 seconds. Power calculations indicate that sample sizes = 11 will yield power of .95 and .80, respectively, to detect a tDCS-induced improvement gait velocity and physical function. However, assuming a very large effect size of greater than 2 is likely unrealistic. Therefore, we based our power analysis on determining a substantial meaningful change in gait speed (0.1 m/s) as determined by Perera et al.⁴⁸ Using a 2 x 3 mixed MANOVA with interaction and an estimated effect size of (Cohen's $d =$

Version 10 Revised 11/21/2014

0.39)³⁷, a conservative $r = 0.60$ ⁴⁹ and an alpha of 0.05 we will need 37 subjects per group to achieve a power of 85%. Therefore, we set our sample size at 88, so our study has sufficient power to detect meaningful changes in gait speed for individuals with chronic stroke.

We set our primary study sample size at 88, so our study has sufficient power to detect a benefit of gait training and to determine if tDCS augments improvement.

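### The sample is defined as 88 completers with attrition replaced, and nothing keeps replaced participants in the analysis (minor: 100 enrolled at 15% attrition yields about 85, not 88)

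*Combined protocol and SAP*

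**What the plan says.** Study Population sets the target: "Up to 100 stroke patients will be enrolled to obtain 88 who meet entry criteria and complete study procedures", split 44 and 44. It then gives the plan's only provision for loss: "Attrition, estimated at about 15%, will be handled by replacement".

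The Protocol Summary puts the number differently: "We will block randomize 88 chronic stroke patients to two treatment arms".

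Randomization Procedures fixes the timing: "After consenting, screening, and obtaining an MRI, participants will be block" randomised to active or sham tDCS. The Study Schedule agrees, placing randomisation in the screening column, ahead of baseline, the 12 treatment sessions and the assessments up to week 8.

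Two other sections anticipate incomplete participation. Compensation offers 75 "dollars for partial completion". The TMS precautions, under Device Risks and again under Protection Against Risks, say that after certain symptoms "the session will be terminated, and the subject will not be tested again".

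Data Analysis (Aims 1-3) takes differences from baseline and applies "A mixed model ANOVA with group (active tDCS groups versus sham tDCS) as the between subjects factor", with assessment time as the within-subject factor. The Power analysis concludes that with "an alpha of 0.05 we will need 37 subjects per group to achieve a power of 85" per cent, and then sets the sample size at 88. The Exploratory Aim also counts 88 people.

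**The concern.** Recruiting extra people to make up numbers does no harm in itself. The harm comes if those they replace drop out of the comparison. The groups compared are then no longer the groups that were randomised, but the subset in each arm who tolerated treatment and stayed to week 8. If active stimulation or poor progress affects who stays, the difference in gait speed, SIS-16 or recruitment-curve slope mixes the treatment effect with selection. Equal loss in the two arms does not rule this out, because different kinds of people may leave each arm.

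The lack of a written rule also leaves the choice of who is analysed open until data have been seen. Interim analyses are planned at unspecified stages, and the person supervising the interventions is not blinded. Blinding of those who collect and analyse the data reduces this risk but does not supply the rule.

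**Working it through.** **Who would be analysed.** Setting the sections side by side:

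1. The sample is made up of people who complete, and attrition is replaced (Study Population).
2. Allocation happens before baseline and treatment (Randomization Procedures, Study Schedule), so attrition during the 4 treatment weeks or follow-up removes randomised people.
3. Data Analysis names no analysis set, gives no rule for missing assessments and does not say that a replaced person's data are kept. A mixed model ANOVA may or may not use partial records, depending on how it is fitted.
4. The power calculation assumes a 2 x 3 mixed MANOVA, which ordinarily needs complete records.

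Followed literally, this gives 44 completers against 44 completers.

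**Form of the bias.** In one arm let p be the share lost and g the amount by which those lost would have gained less than completers. The full-arm mean is (1 - p) x C + p x (C - g) = C - p x g, where C is the completer mean. So completers overstate the arm by p x g, and the bias in the group difference is

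p(active) x g(active) - p(sham) x g(sham).

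With the plan's 15% in both arms this becomes 0.15 x [g(active) - g(sham)]: zero if the gaps are equal, and positive or negative otherwise. The documents give neither g nor attrition by arm, so no value follows. For scale only, a bias as large as the 0.1 m/s meaningful change in the Power analysis would need gaps that differ by 0.1 / 0.15 = 0.67 m/s at equal 15% loss.

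**People involved.** If 88 complete within the cap, at most 100 - 88 = 12 randomised people are lost. If all 100 are randomised and 15% leave, it is 15. If 88 are randomised, it is 88 x 0.15 = 13.2.

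**Counts.** Inputs: 37 per group (Power analysis); 88, 100 and 15% (Study Population).

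- Origin of 88: 37 / (1 - 0.15) = 43.5, rounded up to 44 per arm; 2 x 44 = 88. This reproduces the plan's figure exactly, so 88 may already be 74 inflated for attrition.
- 100 enrolled to 88 completers: 100 x 0.85 = 85. This does not reproduce. For 88 completers, 88 / 0.85 = 103.5, so 104. An attrition of 12% would give 88 from 100.
- If 88 are randomised: 88 x 0.85 = 74.8 expected completers against 2 x 37 = 74 required.
- With independent completion at 85% (binomial): the chance of at least 88 completers from 100 is 0.25, of at least 74 from 100 is 0.999, and of at least 74 from 88 is 0.66.

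**The case against.** The strongest reply is that no sentence says replaced participants are discarded. That is right. A reader might infer that the plan prescribes a completers-only analysis; it does not. Gait is assessed weekly during treatment, so many dropouts would have usable gait data, and a mixed model could include them. Replacement might also mean only people lost before allocation. But the sample is defined by completion, attrition has no other provision, and neither milder reading is written down. What stands is that the completer comparison is the most natural result of the text, not a stated intention.

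The evidence that people will be lost is uneven. Payment for partial completion does not say when people leave. The TMS rule bears on recruitment curves rather than on gait speed or SIS-16, and the risk sections describe seizure and syncope with single-pulse TMS as rare. The 15% estimate carries the point without them.

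On the counts, the plan says up to 100 and about 15%, and the sentence on enrolment may cover screen failures and dropouts together. This makes the mismatch minor, but it does not explain why one section randomises 88 and another requires 88 to complete.

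A likelihood-based model is also not a full cure. It does not remove bias from loss that depends on unobserved outcomes, and it gains no change score from someone without a baseline or any later assessment. Both limits are accepted in the fix.

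**Conclusion.** The point holds as a gap that should be closed. By defining the sample as completers and replacing attrition after an early randomisation, the plan as written most naturally leads to a completer comparison, and nothing in it keeps replaced participants in. This rests on reading attrition as including loss after allocation, which is the likelier reading but is not stated.

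Neither the direction nor the size of any bias can be derived from the documents. A reader might infer that the plan favours active tDCS; nothing in it shows that.

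The count conflict is real but small. A reader might infer that the trial is short of power because 100 cannot be expected to yield 88. Taking the plan's 37 per group as given, that does not follow: 85 expected completers exceed 74. Even if 88 is the number randomised, about 75 are expected, a shortfall of a few would cost little power, and partial records would still contribute under the proposed model.

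**What to change.** In Data Analysis, state that:

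- all randomised participants, including any who are replaced, are analysed in their assigned arm with a likelihood-based mixed model using all available assessments, valid under missing at random;
- participants with no baseline or no post-baseline assessment, who contribute no change score, are counted and reported by arm with reasons;
- completers are a sensitivity analysis.

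In Study Population, say that further recruitment up to 100 does not remove anyone already randomised. In the follow-up section, say that the scheduled week 5 and week 8 assessments are attempted in those who stop treatment, where the protocol's own safety rules allow.

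Reconcile the Protocol Summary, Study Population and Power analysis by saying what 88 is: either the number randomised, with about 75 expected completers against 74 required, or the completer target, in which case 100 enrolled should be expected to give about 85. The choice is the sponsor's, and the cap need not change.

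The cost is protocol wording and some effort to keep people in follow-up. The remaining weakness is that missing at random cannot be verified from the data.
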